### 9.8.2. Withdrawal from Study

If a subject prematurely withdraws from the study, the investigator will record the reason for withdrawal on the relevant eCRF. All subjects who withdraw from the study prematurely will be asked to have all early termination assessments performed.

Reasons for withdrawal from study include, but are not limited to:

- Withdrawal by the subject
- Adverse Event
- Death
- Lost to follow-up
- Site terminated by Sponsor
- Study terminated by Sponsor

- Protocol deviation
- Investigator decision

### 9.8.3. Sponsor's Termination or Pause of Study

The Sponsor reserves the right to discontinue or pause the study overall or at the level of individual sites at any time for clinical or administrative reasons. Study termination must be implemented by the investigator, if instructed to do so by the Sponsor in a time frame that is compatible with the subjects' well-being.

### 10. STUDY TREATMENT

### **10.1.** Study Treatment Supplies

#### 10.1.1. NBI-827104

The Sponsor or its designee will provide the study center with a supply of NBI-827104 minitablets sufficient for the completion of the treatment period of the study.

### 10.1.2. Placebo/Reference Drug

The Study Sponsor or its designee will provide the study center with a supply of matching placebo minitablets sufficient for the completion of the treatment period of the study.

# **10.2.** Study Treatment Storage

Formulated NBI-827104 and placebo minitablets

The investigator should refer to the label of the study treatment for information on the storage conditions.

Study treatment should be stored and inventoried according to applicable local and federal regulations and study procedures.

# 10.3. Study Treatment Packaging and Labeling

Each bottle of NBI-827104 or matching placebo will be supplied with a minitablet dispensing device. Instructions on use of the device for dosing will be provided in the Pharmacy Manual. Study treatment will be labeled to comply with the applicable laws and regulations of the countries in which the study sites are located.

# 10.4. Direct-to-Subject Shipments of Study Treatment

To ensure continued access to study treatment, if a subject is unable to go to the site when study treatment is to be dispensed, study treatment may be delivered from the site's pharmacy to the subject's residence by a distributor independent from the Sponsor. The subject's name, address, and other contact details will not be accessible to the Sponsor, and the distributor will not have access to the subject's health information.

[figure not shown]
# 10.5. Blinding

This study includes up to of double-blind, placebo-controlled treatment during which the subject, investigator, and all study center personnel will be blinded to the subject's treatment. The Sponsor will be blinded except for supply chain personnel who are not involved in decisions regarding subject treatment. During this treatment period, all subjects will receive NBI-827104 or placebo to be self-administered once daily.

The randomization code will be broken for an individual subject only if the subject is pregnant, experiences an SAE that the investigator feels cannot be adequately treated without knowing the subject's treatment assignment, or for regulatory reporting requirements. In the case of a medical emergency in which knowledge of the identity of the study treatment is important for subject management, the investigator has the responsibility for unblinding the randomized treatment assignment using an Interactive Web Response System. It is recommended that the investigator contact the Study Medical Monitor (or designee) before unblinding if it would not result in unnecessary delay to the immediate medical management of the subject. Documentation of the unblinding must be maintained.

Members of the IDMC and individuals who generate the IDMC reports and the independent vendor providing the PK analysis will be unblinded throughout the study.

### 10.6. Study Treatment Preparation and Administration

# 10.7. Study Treatment Compliance and Accountability

Subjects/caregivers will bring all unused study treatment and empty drug packaging material to the center at specified study visits for drug accountability and reconciliation by study center personnel. A compliance check will be performed by weighing the container with the minitablets returned at each study visit.

The quantity of study treatment dispensed, used, and returned will be recorded on a dispensing log or otherwise documented. The quantity of study treatment lost or destroyed must also be accounted for and documented. The designated pharmacist or qualified personnel will be

responsible for maintaining accurate records of the quantity and dates of all study treatment supplies received, dispensed, and returned.

### **10.8.** Study Treatment Return

Returns will be shipped to NBI or its designee at the completion of the study according to instructions provided by NBI or its designee according to applicable state and federal regulations and study procedures.

#### 11. ADVERSE EVENTS

All AEs, whether observed by the investigator, reported by the subject, noted from laboratory findings, or identified by other means, will be recorded from the time the ICF has been signed until the subject's final study visit (or upon early termination).

#### 11.1. Definition

An AE is any untoward medical occurrence in a patient or clinical investigation subject administered a pharmaceutical product and which does not necessarily have to have a causal relationship with this treatment. An AE can therefore be any unfavorable and unintended sign (including an abnormal laboratory finding, for example), symptom, or disease temporally associated with the use of a medicinal product, whether or not considered related to the medicinal product.

AEs include, but are not limited to: (1) a worsening or change in nature, severity, or frequency of conditions present at the start of the study; (2) subject deterioration beyond what would be expected due to primary illness; (3) intercurrent illness; and (4) drug interaction.

All suicidal behaviors and clinically significant suicidal ideations will be documented as an AE.

Subjects should be questioned in a general way, without asking about the occurrence of any specific symptom. The investigator should attempt to establish a diagnosis of the event based on signs, symptoms, and/or other clinical information. In such cases, the diagnosis should be documented as the AE and not the individual signs/symptoms. Following questioning and evaluation, all AEs, whether believed by the investigator to be related or unrelated to the study treatment, must be documented in the subject's medical records, in accordance with the investigator's normal clinical practice and on the AE eCRF. Each AE is to be evaluated for duration, intensity, frequency, seriousness, outcome, other actions taken, and relationship to the study treatment.

The following are not considered AEs:

- Continuous persistent disease/symptom present before drug administration, unless it unexpectedly progresses, or increases in severity following drug administration
- Seizures will not be considered AEs unless there is a significant increase in seizure frequency, there is a new seizure type, occurrence of status epilepticus, and/or in the investigator's opinion it should be captured as an AE.
- Treatment failure or lack of efficacy

- Pregnancy
- Overdose of either study treatment or concomitant medication without any clinical signs or symptoms.

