#### 11.4.1. Definition of a Serious Adverse Event

An SAE is any AE that results in any of the following outcome:

- Death.
- A life-threatening AE. Life-threatening means that the subject was, in the view of the investigator or Sponsor, at immediate risk of death from the reaction as it occurred. It does not mean that hypothetically the event might have caused death if it occurred in a more serious form.
- Inpatient hospitalization or prolongation of existing hospitalization. Hospitalization for elective treatment or a pre-existing condition that did not worsen during the clinical investigation is not considered an AE. Hospitalization or nursing home admission for the purpose of caregiver respite is not considered an AE. Complications that occur during hospitalization are AEs, and if a complication prolongs hospitalization, the event is considered serious. Treatment in a hospital emergency room is not a hospitalization.
- A persistent or significant incapacity or substantial disruption of a person's ability to conduct normal life functions.
- A congenital anomaly/birth defect.
- Important medical events that may not result in death, be life-threatening, or require hospitalization. These events may be considered serious when, based on appropriate medical judgment, they may jeopardize the health of the subject and may require medical or surgical intervention to prevent one of the outcomes listed. Any other event thought by the investigator to be serious should also be reported, following the reporting requirements detailed in this section. Examples of such medical events include allergic bronchospasm requiring intensive treatment in an emergency room or at home, blood dyscrasias, convulsions that do not result in inpatient hospitalization, or the development of drug dependency or drug abuse.

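### The seizure exclusion in Protocol 11.1 omits severity and seriousness, so recording a worsened habitual-type seizure is left to investigator opinion although the general AE definition counts it

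*Protocol*

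**What the plan says.** Protocol 11.1 opens broadly. Among the things it counts as AEs is "a worsening or change in nature, severity, or frequency of conditions present at the start of the study".

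The same section then lists what is not an AE. Two bullets matter here.

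- Persistent disease: "Continuous persistent disease/symptom present before drug administration, unless it unexpectedly progresses, or increases in severity following drug administration". This bullet restores AE status when severity increases.
- Seizures: "Seizures will not be considered AEs unless there is a significant increase in seizure frequency, there is a new seizure type". The sentence continues with "occurrence of status epilepticus, and/or in the investigator's opinion it should be captured as an AE". Severity, duration short of status epilepticus, and seriousness are not among the triggers.

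Protocol 11.4.1 makes seriousness conditional on AE status: "An SAE is any AE that results in any of the following outcome". Three further statements in that section bear on seizures.

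- An admission limit: "Hospitalization for elective treatment or a pre-existing condition that did not worsen during the clinical investigation is not considered an AE".
- A catch-all: "Any other event thought by the investigator to be serious should also be reported".
- An example of an important medical event, which may be serious on medical judgement: "convulsions that do not result in inpatient hospitalization". The section does not say how this applies to a child's habitual seizures.

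SAP 9.2 defines a TEAE to include an event already present that worsens in intensity or in frequency after dosing starts.

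**The concern.** The general definition makes greater severity of a pre-existing condition an AE. The seizure bullet, which is the specific rule a site will apply to a seizure, turns that into an option. The neighbouring bullet on persistent disease kept severity as a trigger, and the documents give no reason for leaving it out for seizures.

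The consequence carries forward. Protocol 11.2 and 11.4.3 require SAEs to reach the sponsor within 24 hours, and SAP 9 and 9.2 build the safety profile on TEAEs and SAEs. A worsened habitual-type seizure that is not entered as an AE reaches neither by default. Worsening of seizures is a natural safety question for a new drug in children with an epileptic encephalopathy. About 24 centres are planned for about 24 children, or roughly one child per centre (24/24 = 1). The judgement would therefore be made by many investigators, each on very few children.

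**Working it through.** No figure in the plan is in question, so the check sets the rules side by side. The inputs are the general AE definition and the two exclusion bullets (Protocol 11.1), the SAE definition with its admission limit, catch-all and convulsion example (Protocol 11.4.1), and the TEAE definition (SAP 9.2). Six cases are run through them.

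1. **Significantly more frequent seizures, a new type, or status epilepticus.** AE under the general definition and under the seizure bullet. No conflict. The visible text gives no threshold for a significant increase.
2. **Habitual type, more severe or longer than baseline, not status epilepticus, no seriousness criterion met.** General definition: AE, because severity has worsened. Seizure bullet: AE only if the investigator thinks so. SAP 9.2: treatment-emergent by its intensity wording, but the SAP can tabulate only what sites enter as an AE. **Conflict.**
3. **As case 2, and a seriousness criterion is met, for example inpatient admission.** General definition plus 11.4.1: AE, therefore SAE. Seizure bullet: no seriousness trigger, so AE status is discretionary and SAE status follows it. The other route is the catch-all in 11.4.1, which also depends on what the investigator thinks. **Conflict.**
4. **Habitual seizure without worsening, followed by admission.** The admission limit in 11.4.1 excludes this expressly. Not recording it follows the protocol. No conflict.
5. **Injury caused by a seizure.** The exclusion covers seizures, not their consequences. The injury is an untoward event in its own right, and an SAE if it meets a criterion. Only the seizure behind it could go unrecorded. No conflict over the injury.
6. **Habitual seizure at baseline pattern, no admission.** Not an AE under 11.1. The convulsion example in 11.4.1 could be read as making it reportable, subject to medical judgement. **Unclear**, because the two sections are not linked.

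The gap is therefore cases 2 and 3, with an ambiguity in case 6.

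The diary does not visibly fill the gap. The seizure measure shown in SAP 4.3.2 is 28 × countable seizures / days with non-missing diary data. It is a count, so one longer or more severe seizure weighs the same as any other. The exploratory endpoints are redacted, so nothing further can be said about them.

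**The case against.** The strongest reply is that nothing is barred from capture. Investigator opinion is itself one of the listed triggers in 11.1, and the catch-all in 11.4.1 speaks of events rather than AEs. An investigator who sees a worrying seizure can report it under either clause, and the general definition supports doing so. This stands, and it limits the point: capture is optional, not prevented. It does not remove the point, because the general definition does not make worsening in severity optional, and two sites could classify the same seizure differently while both follow the text.

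A reader might infer more than the documents support in four ways.

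- *That a seizure which injures a child, or any seizure admission, can escape SAE reporting.* Injuries are AEs in their own right, and admission without worsening is excluded by an explicit rule.
- *That the convulsion example makes an admitted child's seizure serious.* The example describes convulsions that do not lead to admission, and it is subject to medical judgement.
- *That worsened seizures vanish from oversight.* Caregivers keep seizure diaries, and the IDMC reviews safety and tolerability data, not AEs alone. Its charter is not among the documents, so what it receives cannot be judged.
- *That the arms would be compared with bias.* Investigators are blinded. Differing thresholds add noise and may lose events, but no direction between arms can be shown.

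It is also fair to say that the fix leaves some judgement in place, since no baseline measure of seizure severity or duration appears in the visible text.

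**Conclusion.** The inconsistency is real and narrow. For a habitual-type seizure that has worsened in severity or duration short of status epilepticus, including one that then meets a seriousness criterion, Protocol 11.1 contradicts its own general definition and does not match SAP 9.2. Expedited reporting and the TEAE and SAE tables rest for these events on two discretionary clauses. It should be corrected, at low cost.

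The size cannot be derived: the documents give no rate of such seizures and no rate at which investigators would leave them off the AE form. With 24 children split 2:1, the arms are 24 × 2/3 = 16 and 24 × 1/3 = 8, so any single event moves an arm's rate by 1/16 = 6.3 or 1/8 = 12.5 percentage points. That is the weight of any one event in a trial this small. It is not an estimate of what is missed. Nor can all 24 children be assumed to have habitual seizures, since SAP 5.4 tabulates baseline seizures as yes or no.

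The conclusion assumes that sites treat the seizure bullet as the specific rule that overrides the general definition, and that redacted text and the documents not provided (such as the IDMC charter) do not already settle the matter.

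**What to change.** Reconcile Protocol 11.1, Protocol 11.4.1 and SAP 9.2.

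- **Protocol 11.1, seizure bullet:** add that a seizure is also recorded as an AE when it is more severe or longer than the child's baseline pattern, or when a worsened seizure meets any seriousness criterion in 11.4.1.
- **Protocol 11.4.1, convulsion example:** state how it applies to habitual seizures at baseline pattern, so that the two sections give one answer.
- **SAP 9.2:** the TEAE definition already includes intensity. Confirm that it matches the amended bullet.

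This concerns capture and reporting only, not treatment. The cost is a sentence or so in each of the two protocol sections, matching site guidance, and a few more AE and SAE reports. Judging a seizure against the child's baseline pattern will still need the investigator, but recording a seizure judged to be worse would then be required rather than optional.

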### 11.1.1. Intensity of Adverse Events

AEs must be graded for intensity. An intensity category of mild, moderate, or severe, as defined in Table 4, must be entered on the AE eCRF. It should be noted that the term "severe" used to grade intensity is not synonymous with the term "serious."

**Table 4:** Intensity of Adverse Events

Grade	Intensity
Mild	An adverse event that is usually transient and may require only minimal treatment or therapeutic intervention. The event does not generally interfere with usual activities of daily living.
Moderate	An adverse event that is usually alleviated with additional specific therapeutic intervention. The event interferes with usual activities of daily living, causing discomfort but poses no significant or permanent risk of harm to the research subject.
Severe	An adverse event that interrupts usual activities of daily living, or significantly affects clinical status, or may require intensive therapeutic intervention.

### 11.1.2. Relationship to Study treatment

The investigator will document his/her opinion of the relationship of the AE to treatment with study treatment using the criteria outlined in Table 5. An AE is deemed associated with the use of the study treatment "if there is a reasonable possibility that the drug caused the AE" (otherwise referred to as a suspected adverse reaction). Reasonable possibility means there is evidence to suggest a causal relationship between the drug and the AE (Title 21 Code of Federal Regulations [CFR] 312.32 [a]).

**Table 5:** Relationship of Adverse Events to Study treatment

Relationship	Description
Definite	A reaction that follows a reasonable temporal sequence from administration of the drug or in which the drug level has been established in body fluids or tissue; that follows a known or expected response pattern to the suspected drug; and that is confirmed by improvement on stopping or reducing the dosage of the drug, and reappearance of the reaction on repeated exposure.
Possible	An adverse event in which there is reasonable possibility that the drug caused the event. Reasonable possibility means there is evidence to suggest a causal relationship between the drug and the adverse event.
Unlikely	A reaction that follows a reasonable temporal sequence from administration of the drug; that follows a known or suspected response pattern to the suspected drug; but that could reasonably be explained by known characteristics of the subject's clinical state.
Not Related	Any event that does not meet the above criteria.

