### 11.4.4. Expedited Safety Reports

The Sponsor or its representatives will submit an Expedited Safety Report for any suspected adverse reaction (as defined in Section 11.1.2) that is considered both serious and unexpected within 15 calendar days and for any unexpected fatal or life-threatening experience within 7 calendar days to the applicable regulatory authority(ies); or according to country-specific regulations.

The Sponsor or its representatives will send copies of each safety report submitted to regulatory authorities to the investigators. The safety report must be submitted to the appropriate IRB/IEC as soon as possible. Documentation of the submission to the IRB/IEC and receipt by the IRB/IEC (if applicable) must be retained for each safety report.

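### Table 5's 'Unlikely' row overlaps 'Possible' and the protocol's own definition of a suspected adverse reaction, so some serious unexpected events can miss the 15-day report

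*Protocol*

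**What the plan says.** Section 11.1.2 of the Protocol sets the standard in its text. An AE counts as a suspected adverse reaction if there is a reasonable possibility that the drug caused it, and "Reasonable possibility means there is evidence to suggest a causal relationship between the drug and the AE". Investigators then record their opinion using the four rows of Table 5:

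- *Definite* needs supportive timing (or a documented drug level), a matching response pattern, improvement when the drug is stopped or reduced, and return of the reaction on re-exposure.
- *Possible* repeats the general standard: "An adverse event in which there is reasonable possibility that the drug caused the event". It gives no criteria for timing, pattern or alternative cause.
- *Unlikely* needs supportive timing and an event "that follows a known or suspected response pattern to the suspected drug; but that could reasonably be explained by known characteristics"; the characteristics meant are those of the child's clinical state.
- *Not Related* is the remainder: "Any event that does not meet the above criteria".

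Section 11.4.4 refers back to this section. The sponsor "will submit an Expedited Safety Report for any suspected adverse reaction (as defined in Section 11.1.2) that is considered both serious and unexpected"; the deadline for this is 15 days. The same sentence adds a shorter deadline, "for any unexpected fatal or life-threatening experience within 7 calendar days". Copies of submitted reports go to investigators, and each report must be submitted to the IRB/IEC.

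**The concern.** The *Unlikely* row requires two findings that point towards the drug. It then lowers the rating because another explanation is available, and that explanation need only be reasonable, not the more probable one. Having a second explanation does not remove a reasonable possibility that the drug was the cause.

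The overlap matters in this population. Under inclusion criteria 2 and 5, every child has an SWI above 50%, cognitive stagnation or regression, and one to three background antiseizure medications. For neurological and behavioural events, an explanation in the clinical state will often be at hand. Section 5.4 describes this as the first clinical study of the drug's efficacy in children with EECSWS, and only about 24 children are planned. Assessment of individual cases will therefore carry much of the safety information. If an event that should count as a suspected reaction is rated *Unlikely*, authorities may not get the 15-day report, and investigators and IRB/IECs may not get their copies.

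**Working it through.** No arithmetic applies, and the plan gives no figure to reproduce. The check sets the definitions side by side and follows one event through them.

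| Row of Table 5 | Timing fits the drug | Pattern fits the drug | Alternative cause | Reasonable-possibility wording |
|---|---|---|---|---|
| *Definite* | required (or drug level) | required | not mentioned | no |
| *Possible* | not mentioned | not mentioned | not mentioned | yes |
| *Unlikely* | required | required | required, at the level of a reasonable explanation | no |
| *Not Related* | residual | residual | residual | no |

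Take a serious, unexpected event that is neither fatal nor life-threatening. It starts at a plausible time after dosing, fits a suspected pattern for the drug, and could also be explained by the child's disease.

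1. **Against *Unlikely*.** Timing, pattern and alternative explanation are all present, so every element is met.
2. **Against the text of 11.1.2.** The text asks for evidence that suggests causation. Table 5 itself treats timing and pattern as such evidence, because it builds *Definite* on them. The event can therefore meet the text and the *Possible* row.
3. **Tie-break.** None is given. *Unlikely* is the only row that describes this mixed case explicitly, so an investigator working from the table is drawn to it.
4. **Link to reporting.** The 15-day rule applies to suspected adverse reactions as defined in 11.1.2. No section says which rows those are. *Unlikely* ranks below *Possible* and lacks the reasonable-possibility wording, so its natural reading is that it is not a suspected reaction. Section 11.4.3 asks for the investigator's rating with the initial SAE report, and neither document describes a separate causality assessment by the sponsor.
5. **Result.** The event can go unreported under the 15-day rule.

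Changing one feature at a time shows how far the gap extends:

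- If the event is fatal or life-threatening, the 7-day rule applies to any unexpected event and, as written, has no causality condition. There is no gap.
- If the pattern is known rather than suspected, the event may be judged expected and would then not be expedited in any case.
- If there is no known or suspected pattern, the event cannot meet *Unlikely* as written, and this route does not arise.

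The exposed set is therefore events that are serious, unexpected, neither fatal nor life-threatening, mainly of a suspected pattern, and rated *Unlikely*.

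**The case against.** The strongest reply is that the only definition of a suspected adverse reaction in 11.1.2 is its text, not the table. On that reading the event above already meets the definition, and the sponsor should expedite it whatever row was ticked. This has force. No section says that *Unlikely* events are left out of expedited reporting, so the exclusion is an inference. But the protocol does not say that the text overrides the rating either, and it tells investigators to rate by the table.

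Several safeguards also stand. SAEs must reach the sponsor within 24 hours regardless of rating (Sections 11.2, 11.4.2 and 11.4.3). The IDMC reviews safety data on an ongoing basis (Section 9.4.1), and its members are unblinded throughout (Section 10.5). Investigators owe the IRB/IEC reports of SAEs (Section 14.2). What is at risk is onward expedited reporting, not the sponsor's awareness of events during the study.

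A reader might go further and infer that the table takes events out of both the 7-day and the 15-day reports. The wording of the 7-day rule does not support that. A reader might also infer that all 24 children are affected, or that this boundary decides most expedited reports. Inclusion criteria 2 and 5 show that an alternative explanation is often available. They do not count events, and neither document gives an expected number of serious unexpected events.

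No planned analysis depends on the rating: the AE tables listed in SAP Section 9.2 include none by relationship to treatment. For the same reason, none of those tables would reveal misclassification.

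**Conclusion.** The point holds in a limited form. The *Possible* and *Unlikely* rows overlap, *Unlikely* conflicts with the definition in the same section, and the protocol neither resolves the overlap nor links the rows to Section 11.4.4. This is a stated rule that can misclassify events, not merely missing detail.

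The consequence is confined to the 15-day report and its copies, for the exposed set defined above. It rests on two assumptions: that investigators apply the *Unlikely* row as worded, and that the sponsor treats *Unlikely* as outside the definition of a suspected adverse reaction. The documents make both plausible and confirm neither. The number of affected events is unknown and may be small. The point still deserves correction because it concerns safety reporting in children and the repair is minor.

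**What to change.** Make the rows of Table 5 mutually exclusive and consistent with the reasonable-possibility text:

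- An event with supportive timing and a known or suspected drug pattern is rated at least *Possible*, even if the clinical state could also explain it.
- *Unlikely* is kept for events with some temporal association where the overall evidence does not suggest a causal relationship. It must stay distinct from *Not Related*. A wording based only on timing or pattern failing to support the drug would absorb most of that residual row and create a new overlap.
- One sentence is added to 11.1.2: *Definite* and *Possible* are suspected adverse reactions for the purposes of Section 11.4.4.

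The cost is one table row and one sentence in an amendment, plus the matching guidance for completing the AE eCRF. The downside is that more events will be assessed as suspected reactions, with possibly a few more expedited reports. No AE table listed in the SAP needs to change.
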